9.5.3.3 Exploratory Endpoints

Expression of CD3, CD20, CD55, CD68, CD163, CD206, and TE7 biomarkers and their association with TUV_{joint} will be assessed with the Pearson (product-moment) and Spearman (rank) correlation matrices calculated for each measurement of expression (IHC, RNA_{seq}, and [optional] flow cytometry). The marginal distributions will be summarized with descriptive statistics (number of complete data points, means, standard deviations, minima, medians, and maxima). The joint distribution will be presented graphically in a windowpane plot of the scatter diagrams.

Expression of CD206, CD163, and CD68 genes in mRNA will be measured with cDNA probes. The TUV_{joint} values concentrations will be regressed on the mRNA abundance as determined by RNA-seq values. The marginal distributions will be summarized with descriptive statistics (number of complete data points, means, standard deviations, minima, medians, and maxima). The joint distribution will be presented in a windowpane plot of the scatter diagrams. The regression coefficients will be presented with the estimated residual covariance matrix.

The number, size, and co-expression of CD68, CD163, and CD206 expressing macrophages measured by flow cytometry and their relationship with TUV_{joint} will be assessed with the Pearson (product-moment) and Spearman (rank) correlation matrices. The marginal distributions of all variables will be summarized by descriptive statistics (number of complete data points, means, standard deviations, minima, medians, and maxima). The joint distributions will be presented graphically in a windowpane plot of the scatter diagrams.

The ability of TUV_{global} to discriminate among lympho-myeloid, diffuse myeloid, and pauci-immune fibroid RA disease types will be evaluated with a multinomial logistic regression model with TUV_{global} as a covariate. RA type will be the response variable and TUV_{global} will be the explanatory variable. ROC curves will be generated using the lympho-myeloid type as the base class. The marginal distribution of disease type will be summarized with a frequency table, while the marginal distribution of TUV_{global} will be summarized with descriptive statistics (number of data pairs, mean, standard deviation, minimum, median and maximum). The distribution will be graphically summarized with box plots showing the conditional distribution of TUV_{global} for each disease type.

9.5.4 Analysis of Safety Variables

All safety analyses will be conducted on the safety population.

All adverse events (AEs) will be observed for each subject from the time of signing of informed consent until study completion. A treatment-emergent AE (TEAE) is defined as an AE whose start date is on or after the date of the first tilmanocept injection. If the first injection date or the AE start date is missing, the AE will be considered treatment emergent.

Prior to analysis all AEs will be coded using the MedDRA coding dictionary. Based on the coded terms, TEAEs will be summarized as follows:

- By system organ class (SOC) and preferred term (PT);
- By SOC and PT and relation to the study drug;
- By SOC and PT and severity.

Observed and change from baseline for vital sign parameters, ECG parameters, hematology, clinical chemistry, and urinalysis parameters will be summarized using descriptive statistics (n, mean, standard deviation, minima, median, and maximum) at each time point.

A data listing will be prepared that reflects the occurrence of TEAEs associated with each concomitant medication or class of medications to examine whether a drug interaction signal is detectable.

Other safety analyses may be described in the SAP for the study.

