7.1.2 Visit 2, Tc 99m Tilmanocept Administration and Imaging (Day 0)

Pre-Tc 99m Tilmanocept Administration

The following procedures will be completed for all subjects on the day of injection prior to the administration of Tc 99m tilmanocept:

- A urine pregnancy test for women of child-bearing potential. Females of child bearing potential are defined as women that are not surgically sterile (hysterectomy or bilateral oophorectomy) nor postmenopausal for at least 1 year prior to screening. Women who are not of childbearing potential will not require a pregnancy test.
- Assessment of AEs
- Concomitant medication review
- ECG (see [Section 8.7.3](#)) within 30 minutes prior to administration of Tc 99m tilmanocept
- Vital signs after at least 1 minute in a resting position (body temperature, heart rate, blood pressure, and respiratory rate) within 30 minutes prior to administration of Tc- 99m tilmanocept

Tc 99m Tilmanocept Administration

IV administration of Tc 99m tilmanocept will be at study time 00:00. The preferred site of IV placement will be the left or right antecubital vein. The filled syringe will be connected to the catheter for a slow push injection. At the completion of the injection, a 10-mL sterile normal saline flush will be administered. The IV administration will be performed in the Nuclear Medicine Department by an onsite Certified Nuclear Medicine Technologist or Nuclear Medicine Physician. Subjects will be continuously monitored for AEs.

0 to 30 Minutes Post-Tc 99m Tilmanocept Administration

- Assessment of AEs
- ECG (completed before vital signs)
- Vital signs after at least 1 minute in a resting position (body temperature, heart rate, blood pressure, and respiratory rate)

60 to 75 Minutes Post-Tc 99m Tilmanocept Administration

- Assessment of AEs
- Image acquisition: Static gamma camera scan of the bilateral hands and wrists
- Clinical Labs (at conclusion of the imaging session)

7.1.3 Visit 3, Follow-up Telephone Safety Assessment (24 to 72 hours post-Tc 99m tilmanocept administration)

- Review of concomitant medications
- Assessment of AEs

7.1.4 Visit 4, Synovial Tissue Biopsy (Day 3 to 7 post-Tc 99m tilmanocept administration)

- Ultrasound assessment of synovitis
- Ultrasound-guided synovial tissue biopsy of selected joint in accordance with [Table 4](#)
- AE assessment
- Review of concomitant medications

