8.7 Safety

8.7.1 Adverse Events

8.7.1.1 Definition of Adverse Event

The definitions below follow International Conference on Harmonization (ICH) – Good Clinical Practice (GCP) (see also ICH Guideline for Clinical Safety Data Management: Definitions and Standards for Expedited Reporting).

An AE is defined as any untoward medical occurrence in a subject administered a pharmaceutical product and which does not necessarily have a causal relationship with this treatment. An AE can therefore be any unfavorable and unintended sign (including an abnormal laboratory finding), symptom, or disease temporally associated with the use of a medicinal (investigational) product, whether or not considered drug related.

Any clinically significant change in a condition (worsening) from screening that results in a change in subject management will be considered an AE and will be recorded on the AE page of the CRF.

For this study, all untoward medical occurrences beginning on the Visit 2 (Day 0) until the final Follow-up Telephone Safety Assessment (Visit 5) are to be reported as AEs. AEs continuing after study completion will be followed to normalization or stabilization. Additionally, untoward medical events occurring prior to the day of Tc 99m tilmanocept administration will be collected and added to the subject's medical history unless they are related to a study procedure in which case the event will be recorded as an AE. SAEs will be reported from the time of consent through the end of participation.

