8.7.1.3 Assessments and Documentation of Adverse Events

Attention shall be paid to the occurrence of AEs for the duration of subject participation. Events occurring prior to Visit 2 (Day 0) will be recorded in the subject's medical history unless they are related to a study procedure in which case the event will be recorded as an AE. Untoward medical events beginning on Visit 2 (Day 0) through the completion of the Visit 5 Follow-up Telephone Safety Assessment will be reported as adverse events. SAEs will be reported from the time of consent through the end of participation.

Any AE (observed, volunteered, or elicited) should be recorded in detail in the source documentation.

The following information is required:

- The **date and time of onset** of any AE.
- The **duration** (the entire duration of an event or symptom, calculated from date of onset to date of end, if not recorded directly).
- The **seriousness** of the AE will be assessed by the investigator. If the investigator deems that an AE qualifies as an SAE, a special form provided by the sponsor should be completed and the event must be immediately reported to the sponsor. A definition of serious adverse events is provided in [Section 8.7.1.5](#).
- The maximum **severity** (mild, moderate, or severe).
- If drug treatment was administered for the event, specific concomitant medication must be documented.
- The **relationship** of the AE to the investigational product and to study conduct (for definitions, see above).
- The **outcome** of the AE (resolved, resolved with sequelae, not resolved, unknown, death).

AEs will be coded according to an internationally recognized dictionary (Medical Dictionary for Regulatory Activities [MedDRA]).

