## 5.0 Analysis of Safety

### 5.1 Description of Safety Variables

The safety analysis variables are defined as follows:

- Adverse Events (AEs)
- Clinical Laboratory Tests (hematology, serum chemistry, urinalysis)
- ECG Parameters
- Vital Signs

All adverse events (AEs) will be observed for each subject from the time of signing of informed consent until study completion. A treatment-emergent AE (TEAE) is defined as an AE whose start date is on or after the date of the first tilmanocept injection. If the first injection date or the AE start date is missing, the AE will be considered treatment emergent.

Prior to analysis to all AEs will be coded using the MedDRA coding dictionary. Based on the coded terms, TEAEs will be summarized as follows:

- By system organ class (SOC) and preferred term (PT);
- By SOC and PT and relation to the study drug;
- By SOC and PT and severity.

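### The treatment-emergent rule uses calendar date only, so an AE that began on Day 0 before the single injection counts as a TEAE, although both clock times are recorded

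*Protocol*

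**What the plan says.** The definition is the same in both documents. Protocol 9.5.4 defines a TEAE as "an AE whose start date is on or after the date of the first tilmanocept injection", and SAP 5.1 repeats that sentence word for word. Protocol 9.5.4 adds a default, which SAP 5.1 also repeats: "If the first injection date or the AE start date is missing, the AE will be considered treatment emergent". Neither document says how to treat an event on the day of injection, or one with a known date but a missing time.

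Four other parts of the plan bear on that day:

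- **Schedule.** Protocol 7.1.2 lists an AE assessment, an ECG and vital signs among the procedures to be done "on the day of injection prior to the administration of Tc 99m tilmanocept". There is a single injection (Protocol 5.3).
- **AE window.** Protocol 8.7.1.1 and 8.7.1.3 report as an AE anything untoward that begins on Day 0. The cut-off with medical history is the visit day, not the injection: "Events occurring prior to Visit 2 (Day 0) will be recorded in the subject's medical history", unless the event is related to a study procedure.
- **Times collected.** Protocol 8.7.1.3 requires the "date and time of onset" of any AE. SAP Data Listing 23 carries the date and time of injection. Data Listings 11 and 12 set AE start date and time beside those of the nearest previous injection.
- **Output.** The SAP's AE tables, 55 and 56, cover TEAEs only. The protocol synopsis plans to tabulate AEs as well as TEAEs.

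**The concern.** A TEAE count is meant to cover events that arise after exposure. Here the rule lets in events that came before the only exposure, and the plan looks for AEs in exactly that interval. Protocol 8.7.2, for example, makes a clinically significant worsening of vital signs from screening an AE if it changes the subject's management, and one set of vital signs is taken within 30 minutes before injection.

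The rule also sits badly with two other parts of the SAP. The vital signs text in section 5.2 makes the pre-injection values the baseline for the post-injection ones, so one pre-injection finding could be baseline in Table 52 and treatment-emergent in Tables 55 and 56. Data Listing 12 lists TEAEs with the time of the nearest previous tilmanocept injection. A TEAE that began before the only injection has no such time.

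What is at stake is the accuracy of the crude TEAE counts. AE incidence is part of the safety objective (Protocol 2.4), and in a study of this size one subject is visible in a percentage.

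**Working it through.** **Classification.** The plan states no figure to reproduce, so the check sets its rule beside a rule based on date and time.

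| AE onset | Plan (date only) | Date and time |
|---|---|---|
| Before Day 0 | not a TEAE | not a TEAE |
| Day 0, before injection | **TEAE** | **not a TEAE** |
| Day 0, at or after injection | TEAE | TEAE |
| Day 0, time missing | TEAE | TEAE (by default) |
| Start date missing | TEAE | TEAE (existing default) |

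Only the second row changes. The start date equals the injection date, so the condition of being on or after that date is met whatever the time. The two times that would settle the matter are both collected.

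**Size.** Inputs:

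- Planned size of about 12 to 24 joints, with a final sample of at least 12 (Protocol 9.4, SAP 1.3). One joint is biopsied per subject.
- Biopsy fails to give enough tissue in about 15% of cases (same sections).
- The safety population is everyone injected, regardless of imaging or biopsy (SAP 2.2), so it can exceed the number of evaluable joints.

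If N subjects are injected and one of them has a pre-injection Day 0 event as the only TEAE, incidence rises by 1/N:

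- N = 12: 1/12 = 8.3 percentage points.
- N = 24: 1/24 = 4.2 points.
- If failed biopsies are replaced to reach 24 evaluable joints: 24/0.85 = 28.2, rounded up to 29, and 1/29 = 3.4 points.

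These are ceilings per affected subject. If that subject also has a TEAE after injection, including one after the biopsy, the proportion with at least one TEAE does not move. Only the event count and the organ-class or preferred-term rows of Table 56 can change.

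**The case against.** The best defence is that the rule is coherent and cautious. AE collection also works by day, missing dates default to treatment-emergent, and any error overcounts. The study is open-label and single-dose with no control arm, its safety summaries are descriptive, and no test or stopping rule in the documents uses the TEAE count. Anyone reading Listings 11 and 12 can find an affected event. All of this stands. It limits the importance of the point but does not make the label correct.

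Some stronger readings are tempting, and the documents do not support them:

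- **That every event found at the pre-injection check becomes a TEAE.** The rule turns on onset. An event found then that began before Day 0 is not a TEAE unless its start date is missing.
- **That the tables attribute pre-injection events to the tracer.** TEAE status concerns timing only. The investigator rates relationship to drug and to procedure on separate five-level scales (Protocol 8.7.1.2), and Table 55 reports both. A pre-injection event would be expected to be rated as not drug-related.
- **That Day 0 makes up a large part of the observation time.** Follow-up runs to Visit 5, which is biopsy on Day 3 to 7 plus 5 ± 2 days, so about Day 6 to Day 14. Only the hours of Day 0 before injection matter here.

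A further objection is that a change to the definition alone would take pre-injection AEs out of every SAP table and leave them only in Listing 11. That is right, and the fix has to deal with it.

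**Conclusion.** The point holds in a limited form. Followed as written, both documents label an AE that began on Day 0 before the single injection as treatment-emergent, and the data to avoid this are already collected. The consequence is a possible conservative inflation of the crude TEAE counts in Tables 55 and 56. No efficacy result is affected.

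A reader might take the 8.3 to 4.2 points as the expected bias. They are the most that one affected subject can add, on the assumption that 12 to 24 subjects are injected. The figure of 3.4 points assumes that 29 are injected. The documents give no expected number of such events, and it may be zero.

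**What to change.** In SAP 5.1, and in Protocol 9.5.4 at the next amendment:

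1. Define a TEAE as an AE whose onset date and time are at or after the date and time of injection.
2. If onset is on Day 0 and the time is missing, count the event as treatment-emergent.
3. Keep the existing default for a missing AE start date or injection date.
4. Report AEs with onset before injection in a separate non-TEAE row or table. This fits the synopsis plan to tabulate AEs as well as TEAEs. It also gives a place to procedure-related AEs that began before Day 0, which no SAP table now shows.

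The cost is a one-sentence edit and one extra row or table, with no new data. Protocol 3.3 requires a formal amendment for changes that are not purely administrative, so the protocol wording can wait for an amendment made for other reasons. This is a cheap improvement of lowest priority.

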9.5.5 Handling of Missing Values

The analysis of the efficacy and safety variables will be carried out on the observed data, i.e., a complete case analysis. For the regression and correlation analyses, a subject must have valid values for all variables to be used in the analysis.

9.5.6 Interim Analysis

An interim analysis will be performed after 4 subjects in each of the 3 pathotypes (diffuse myeloid, lympho-myeloid, and pauci-immune fibroid) have been imaged. Specific analyses will be described in the study SAP (or interim analysis plan [IAP]) and will include computation of the product-moment and rank correlations between TUV_{joint} and CD206 expressing macrophage count (defined in [Section 9.5.3.1](#)). Additional analyses may be described in the study IAP (if written) or SAP (if no IAP is written). The final sample size will be recalculated after completion of the interim analysis.

10 DATA HANDLING AND QUALITY ASSURANCE

10.1 Data Recording

Data required according to this protocol are captured in the subject's source documentation and are to be entered onto the eCRFs (provided by the sponsor) as soon as possible.

10.1.1 CRF Design

eCRFs will be used for collecting all data generated during the trial. CRF completion details will be documented in a separate document that will be provided by the sponsor and maintained in the trial master file (TMF).

10.2 Monitoring

This study will be monitored regularly by a clinical research associate (CRA) from the sponsor or a contract research organization (CRO). Monitoring procedures include 1 or more visits designed to clarify all prerequisites before the study starts. Interim monitoring visits will take place on a regular basis according to a schedule fixed by mutual agreement. During these visits, the CRA will check for completion of the entries on the CRFs, their compliance with the protocol and with GCP, and will compare the CRF entries with the source data.

All data recorded in the CRF will be captured in the source documentation.

The CRA will verify the correct use of the investigational product. The investigational product will not be supplied to the investigator site prior to a favorable opinion from the IRB/IEC and the regulatory authority and, if appropriate, from the radiation protection authorities. In addition, the CRA will determine whether all AEs or SAEs have been appropriately reported (including adherence to the time periods required for SAEs).

10.3 Data Processing

Study data documentation will be maintained specifying all relevant aspects of data processing for the study (including data validation, cleaning, correcting, releasing). This documentation will be stored in the TMF.

For data coding (e.g., AEs, medication, medical/surgical history), internationally recognized and accepted dictionaries will be used. These and the processes used for coding will be specified in the data management plan

10.4 Auditing

A member of the sponsor's (or a designated CRO) quality assurance unit may arrange to visit the investigator in order to audit the performance of the study at the study site and the study documents originating there. The auditor(s) will usually be accompanied by a CRA or the study team leader. The investigator will be informed about the outcome of the audit.

In addition, inspections by health authority representatives and IRB(s)/IEC(s) are possible at any time. The investigator is to notify the sponsor of any such inspection immediately.

10.5 Archiving

Essential documents shall be archived safely and securely in such a way that ensures that they are readily available upon authorities' request. Patient (hospital) files will be archived according to local regulations and in accordance with the maximum period of time permitted by the hospital, institution, or private practice. Where the archiving procedures do not meet the minimum timelines required by the sponsor, alternative arrangements must be made to ensure the availability of the source documents for the required period.

The investigator/institution notifies the sponsor if the archival arrangements change (e.g., relocation or transfer of ownership).

The investigator site file is not to be destroyed without the sponsor's approval.

The investigator's contract will contain all regulations relevant for the study center.

10.6 Premature Termination of the Study

10.6.1 Termination by the Sponsor

The sponsor may terminate the study at any time for any of the following reasons:

1. Failure to enroll subjects
2. Protocol violations
3. Inaccurate or incomplete data
4. Unsafe or unethical practices
5. Questionable safety of the investigational product
6. Suspected lack of efficacy of the investigational product
7. Administrative decision

10.6.2 Termination by the Investigator

If the investigator terminates the study prematurely, the investigator must do the following:

- Return all unused investigational products and related study materials to the sponsor.
- Provide the IRB(s)/IEC(s) and the sponsor with a written statement describing why the study was terminated prematurely. Prompt compliance with this requirement is essential so that the sponsor may comply with its regulatory obligations.

10.6.3 Study as a Whole

The sponsor retains the right to prematurely terminate the study as a whole at any time.

At the discretion of the sponsor, the entire study may be canceled for medical reasons. In addition, the sponsor retains the right to end the study at any time if the study cannot be carried out as agreed upon in the protocol. In case of early termination or suspension of the study, the principal investigator/sponsor will promptly inform the investigator/institutions, regulatory authorities, and IRB/IEC of the termination or suspension and the reason for that.

10.6.4 Center

At any time, the study may be terminated at an individual center if:

- The center cannot comply with the requirements of the protocol.
- It is not possible for the center to comply with GCP standards.

10.6.5 Study Participant

Individual subjects may be withdrawn from the study according to the criteria specified in [Section 4.5](#)

11 ETHICAL AND LEGAL ASPECTS

11.1 Ethical and Legal Conduct of the Study

The planning and conduct of this clinical study are subject to national laws. Only when all the requirements of the appropriate regulatory authority have been fulfilled will the study begin. The study will be conducted in accordance with the ethical principles that have their origin in the Declaration of Helsinki and the ICH-GCP Guidelines of 17 Jan 1997. At the discretion of the investigator, the entire study may be canceled for medical reasons. In addition, the sponsor retains the right to end the study for medical-scientific or GCP-relevant reasons. In case of premature termination, the investigators, IRB(s)/IEC(s) and Regulatory Authorities will be informed by the Study Manager. As required by local law, current safety-relevant information will be provided to the IRB(s)/IEC(s) and the regulatory authorities by the sponsor. The sponsor will also inform all investigators about relevant safety events according to the applicable regulations.

